Time to recovery with WHO Scale score  $\leq 3$  and without supplemental oxygen will be analyzed based on mITT and EE Set.

*Proportion of patients achieving recovery by Day 14 and by Day 28*

Number and percentage of patients achieving recovery (WHO scale score  $\leq 3$  or discharge from hospital, whichever occurs first) by Day 14 and by Day 28 will be presented.

*Duration of supplemental oxygen (O2) requirement :*

The number of days with supplemental oxygen (O2) will be calculated as:

stop date of supplemental oxygen – start date of supplemental oxygen +1; if supplemental oxygen started after study drug administration; otherwise supplemental oxygen – date of study drug administration +1.

If there are multiple periods of supplemental oxygen (O2), total days will be the sum of each period. Patients who die or withdraw from the study with ongoing supplemental oxygen at the last contact date, days will be (earliest of [date of death, EOS date] – start date of supplemental oxygen +1). Standard descriptive statistics (mean, SD, median, minimum, maximum) will be used. Standard descriptive statistics will also be presented for mITT Set excluding withdrawals and deaths.

Days of supplemental oxygen (O2) up to Day 14 will be used as a sensitivity analysis. Days will be calculated as below:

- For patients who Die or Withdraw before Day 14, their total will be factored-up to an equivalent 14 day period. For example, if a patient withdraws on Day 5 having already received 3 days of supplemental oxygen between Day 1 and Day 5, then their endpoint value will be 8.4 days i.e.  $(3/5)*14$  .
- For patients who do not withdraw or die before Day 14, count the actual days on supplemental oxygen (O2) up to Day 14.

*Number of days with fever (temperature  $>100.4^{\circ}\text{F}$  [ $38.0^{\circ}\text{C}$ ]):*

The Number of days with fever are calculated as:

stop date of fever – start date of fever +1, if fever started after study drug administration; otherwise stop date of fever – date of study drug administration +1.

If there are multiple periods of fever, Total days will be the sum of each period. Standard descriptive statistics (mean, SD, median, minimum, maximum) will be used. Standard descriptive statistics will also be presented for mITT Set excluding withdrawals and deaths.

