Days with fever up to Day 14 will be used as a sensitivity analysis. Days will be calculated the same as described for Days of supplemental oxygen (O2) up to Day 14.

Change from baseline in WHO Ordinal Scale score

The description of the WHO Ordinal Scale score is shown in [Section 6.2](#). The Number and percentage of patients on WHO Scale scores and change from baseline (-7, -6, -5, -4, -3, -1, 0, 1, 2, 3, 4) will be presented by visit. Shift table will be presented by visit as well.

Simple Ordinal logistic regression on the WHO Scale score at each visit (Days 5, 7, 14, 28, and 60) will be performed to compare ATYR1923 1 mg/kg versus Placebo and ATYR1923 3 mg/kg versus Placebo. Firth logistic regression ([Firth, 1993](#)) on the collapsed WHO Ordinal Scale (0-3 versus 4-8) at each visit (Days 5, 7, 14, 28, and 60) will be performed as well.

Distribution of WHO Ordinal Scale at 1, 2, 3, 4, 5, 6, 7, 10, 14, 28 and 60 days will be visualized by treatment group using an stacked bar chart. These figures will only consider scheduled assessments and in case the scheduled assessment is not available the mapped unscheduled TC follow up assessments as defined in [Section 4.2](#).

Time to Improvement in Clinical Status

Time to improvement in days is the time in which the patient sees a decrease after study treatment in the WHO Ordinal Scale score from baseline by at least 1 point, derived as:

date of decrease in WHO scale compared to baseline by at least 1 point - study drug administration date; or date of discharge from hospital - study drug administration date, whichever occurs first.

In the case that a patient has not decreased in the WHO scale or withdraws from the study, they will be censored at EOS date. Time to improvement will be analyzed using the Kaplan-Meier methods and Cox Proportional Hazards model as described in the above.

Repeat analysis above for improvement of WHO Ordinal Scale score by at least 2 points.

Additionally, time to improvement will be analyzed using an adapted derivation: date of decrease in WHO scale compared to baseline by at least 1 point - randomization date; or date of discharge from hospital - randomization date, whichever occurs first.

Related output will be noted as sensitivity analysis.

Time to improvement (by at least 1 and 2 points) will be analyzed based on mITT and EE Set. Sensitivity analysis for time to improvement will be analyzed based on mITT only.

*All-cause mortality*

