#### 4.9.4.2 Exploratory Efficacy Analyses

Unless specified, standard descriptive statistics (mean, standard deviation, median, minimum, maximum) will be used to summarize continuous variables below. Number and percentage will be presented for categorical variable below. For the number of days, will count the actual days not considering discontinuation or death.

*Change from baseline in supplemental oxygen requirement at day 3, 5, 10, 14 and discharge*

Subject's status of supplemental oxygen requirement (none, low flow: face mask or nasal canula, high flow: high-flow oxygen or non-invasive ventilation) will be summarized at each scheduled visit. Shift to baseline table will be provided for each scheduled visit as well.

By-patient listings of all supplemental oxygen use including unscheduled assessments will be provided.

*Proportion of patients requiring intubation, and among those patients, number of days of intubation.*

Proportion of patients requiring intubation, and among those patients, number of days of intubation derived as:

date of extubating or EOS, whichever occurs first – date of intubation + 1, if intubation happened after study drug administration.

By-patient listings of all respiratory support including unscheduled assessments will be provided.

*Pharmacodynamics (PD) biomarkers and potential COVID-19 disease biomarkers*

See [Section 4.11.3](#).

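### The oxygen and fever day counts in SAP 4.9.4.1 do not reliably treat death as a bad outcome

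*SAP*

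**What the plan says.** SAP 3.4.2 lists duration of supplemental oxygen and number of fever days among the secondary endpoints. SAP 4.9.4.1 plans descriptive statistics only for both, in three versions.

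- **Main count, oxygen.** Periods are summed, and oxygen already running at dosing is counted from the dosing date. A separate formula applies to "Patients who die or withdraw from the study with ongoing supplemental oxygen at the last contact date": it runs from the oxygen start date to the earlier of death and end of study.
- **Main count, fever.** Each period is stop date minus start date plus one. "If there are multiple periods of fever, Total days will be the sum of each period". There is no rule for fever still present at death, and SAP 4.3.1 does not impute other missing data.
- **Second summary, both endpoints.** "Standard descriptive statistics will also be presented for mITT Set excluding withdrawals and deaths".
- **Day 14 sensitivity analysis.** For patients who die or withdraw before Day 14, "their total will be factored-up to an equivalent 14 day period". The worked example is a patient who leaves on Day 5 after 3 oxygen days: "then their endpoint value will be 8.4 days i.e". All other patients get their actual days up to Day 14. Fever follows the same rule: "Days will be calculated the same as described for Days of supplemental oxygen".

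Mortality at Days 14, 28 and 60 is a separate secondary endpoint, shown only as a listing if there are 3 or fewer deaths in total.

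**The concern.** Fewer days is the favourable direction, but a patient who dies stops adding days. A count that ends at death can therefore be short because the patient died. Leaving deaths out of the second summary removes the unfavourable outcome without scoring it. The Day 14 rule scales by the fraction of observed days on oxygen or with fever and ignores the state in which the patient left, so death and withdrawal in good condition are treated alike.

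At stake is how the duration tables read by arm. With about 10 patients per arm, one early death can move a mean in the direction that looks like benefit, and the planned sensitivity analysis corrects this in some cases only.

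**Working it through.** **Inputs.** 30 patients randomised 1:1:1, so about 10 per arm (SAP 3.1.4). The counting rules are those of SAP 4.9.4.1. The documents give no survivor durations, so 9 days is an assumption, with a range of 5 to 14 days below.

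**The SAP's own figure.** Score = (days on / day of exit) × 14. With 3 days and exit on Day 5: (3/5) × 14 = 8.4, as stated.

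**Main oxygen count.** Ten survivors at 9 days give a mean of 9.0. Replace one of them by a patient on oxygen who dies on Day 3:

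| How the death is counted | Days for that patient | Arm mean | Median |
|---|---|---|---|
| From dosing | 3 | (9×9 + 3)/10 = 8.4 | 9 |
| SAP formula for deaths read literally, oxygen begun 3 days before dosing | 3 + 3 = 6 | (81 + 6)/10 = 8.7 | 9 |
| Same, oxygen begun 7 days before dosing | 3 + 7 = 10 | (81 + 10)/10 = 9.1 | 9 |
| Excluded (second summary) | none | 81/9 = 9.0 | 9 |
| Day 14 rule | (3/3) × 14 = 14 | (81 + 14)/10 = 9.5 | 9 |

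Counted from dosing, the fall in the mean is (survivor days − 3)/10. It runs from 0.2 day if survivors have 5 days to 1.1 days if they have 14, and is 0.6 day at 9.

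**Day 14 rule.** Let k be the days on oxygen and d the day of death. The score is 14k/d.

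- If k = d (oxygen every day until death), the score is 14, the maximum: 3/3, 5/5 and 10/10 all give 14. No survivor scores worse.
- If k < d, the score is below 14, and any survivor with more than 14k/d days ranks worse than the death. With k = 3 and d = 10, (3/10) × 14 = 4.2, better than a survivor with 5 or more oxygen days. With k = 3 and d = 5, the score is 8.4, better than a survivor with 9 or more.

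**How k < d can arise.** Protocol 8.3.2 lists intubation and mechanical ventilation among the methods of oxygenation. The oxygen categories in SAP 4.9.4.2 are none, low flow and high flow, without intubation. The duration endpoint does not say which view applies. If ventilator days are not counted, a patient on oxygen on Days 1 to 3, intubated on Day 4 and dead on Day 10 has k = 3, d = 10 and a score of 4.2.

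**Fever.** An afebrile patient who dies on day d scores 0 in the main count and (0/d) × 14 = 0 in the Day 14 analysis, the best possible value in both. One fever day and death on Day 10 gives (1/10) × 14 = 1.4, better than a survivor with 2 or more fever days.

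**Withdrawals.** The 8.4 in the SAP example is the same whether the patient left on or off oxygen. Carrying the last status through Days 6 to 14 would give 3 + 9 = 12 if on oxygen and 3 + 0 = 3 if off.

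**The case against.** The strongest reply is that death is not ignored. It is score 8 on the WHO scale and enters the ordinal regression. It falls in the unfavourable group of the collapsed 0–3 versus 4–8 analysis. A patient who dies without recovering stays in the denominator for recovery by Day 14 and Day 28 (SAP 4.3.1). Mortality is an endpoint of its own. The day counts are untested, safety is primary, and SAP 4.9.2 calls all comparisons exploratory. A fever count of 0 in an afebrile patient is also a correct count. All of this stands and limits the impact. It does not correct the day counts, and up to 3 deaths in 30 patients (10%) would leave no mortality table by arm beside them.

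Some stronger readings are tempting but not supported:

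- A reader might infer that every planned version rewards early death. The Day 14 rule gives the maximum of 14 for death on continuous oxygen, and the Day 3 death above raises the arm mean to 9.5.
- A reader might set a death on Day 5 after 2 oxygen days, (2/5) × 14 = 5.6, against the SAP's 8.4 and conclude that death beats recovery by 2.8 days. That compares two early exits. A patient who recovers and goes home is followed by telephone and is not a withdrawal; with 3 oxygen days the score is 3.
- A reader might assume that the Day 14 analysis was designed to handle death. The SAP calls it a sensitivity analysis and gives no further purpose.

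**Conclusion.** The point holds in a limited form. The main oxygen count ends at death, the second summary omits deaths, and the Day 14 rule can rank a death ahead of a survivor whenever days on oxygen or with fever are fewer than days alive.

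In the main count the effect is a fall in the arm mean of 0.6 day for one Day 3 death. This assumes 10 patients per arm, survivors at 9 days and counting from dosing. It shrinks to 0.3 day if oxygen began 3 days before dosing and the formula for deaths is read literally, and reverses to a rise of 0.1 day if it began 7 days before. The median does not move. The difference in start point between deaths and other patients is an inconsistency that raises some death counts, not a safeguard.

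Under the Day 14 rule the inversion needs oxygen-free or fever-free days before death. It is easier to reach for fever, and for oxygen if ventilator days are left out. The documents do not show how often this would occur. Because the endpoints are descriptive and exploratory, the consequence is a misleading table rather than a wrong formal conclusion.

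**What to change.** - **Day 14 sensitivity analysis (oxygen and fever).** Give 14 days to any death before Day 14 instead of factoring up. For withdrawals, carry the status at last contact to Day 14.
- **New summaries.** Add days alive and free of supplemental oxygen to Day 28, with deaths set to 0, and a matching summary of days alive without fever. Derive the oxygen measure from recorded oxygen start and stop dates and state that ventilator days count as oxygen days. A WHO score of 3 or less will not serve: SAP 4.9.4.1 notes that some patients were discharged still using oxygen, and scheduled scores are not daily after Day 7.
- **Main oxygen count.** Use one start point, the dosing date, for deaths and survivors.
- **Keep** the raw duration tables as description.
- **Label** the new summaries as post-unblinding and post hoc. The SAP revision history already records post-unblinding changes in versions 2.0 and 3.0, and SAP 3.2 requires analyses added after database lock to be marked as post hoc.

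The cost is SAP wording and simple derivations from data already collected. The downsides are that the new measure mixes death with duration, which is why the raw tables should stay beside it, and that it is added after unblinding.

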### 3.1.1 Hospitalized, Non-intubated Patients

**While hospitalized**, non-intubated patients will have study assessments performed on Days 2, 3, 4, 5, 6, 7, 10, and 14 and/or Discharge.

If the non-intubated patient is discharged prior to Day 14, the assessments scheduled for Day 14 and/or discharge will be completed at the time of discharge. If discharge occurs on another scheduled study assessment day (ie, any day between Days 2 and 10), the Day 14 and/or discharge assessments supersede that study assessment day and the patient then will proceed to outpatient telephone contact (TC) follow-up visits. If a patient is discharged prior to Day 14, then outpatient TC follow-up visits are to be conducted on Day 7 (as applicable) and Day 14.

If the non-intubated patient is discharged on Days 15-20, the patient is to have the assessments scheduled for Day 14 and/or discharge performed on the day of discharge. If the patient is hospitalized for  $\geq 21$  days, the Day 14 assessments are to be performed weekly (Days 21, 28, 35, etc.) until discharge (with the exception of pharmacokinetics [PK], which is to be done only at Day 28). After discharge, the patient will proceed to the next scheduled outpatient TC follow-up visit. (Thus, if a patient remains hospitalized on Day 28, the Day 28 TC follow-up visit need not be conducted.)

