**Table 3 Analysis Visit Window for unscheduled Discharge visits**

mapped to	Visit Window
Day 7	Day 8
Day 10	Day 10 ± 1 days
Day 14	Day 14 ± 2 days
Day 28	Day 28 ± 5 days
Day 60	Day 60 ± 5 days

In case several outcomes are available for the nominal/scheduled analysis visits, the latest non-missing result will be used for summaries.

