## **4.3 Missing Data**

### **4.3.1 Imputation of Non-Date Missing Data**

Missing data occurs when any requested data is not provided, leading to blank fields on the collection instrument. These data will be indicated by the use of a “blank” in subject listing displays. Answers such as “Not applicable” and “Not evaluable” are not considered to be missing data and should be displayed as such.

Subjects with the designation of treatment relationship for AEs and SAEs missing will have the worst realistic case assumed to impute the relationship: if relationship is missing and the AE started on or after study drug administration it will be assumed to be “related” (worst case). If the AE with missing relationship started before study drug administration (eg, during Screening Period), it will be considered as “not related” (realistic case). Missing Severity will be assumed to be “Life-threatening” (worst case). In listings these imputed relationships and causalities will be flagged.

For variables which determine the proportion of events, all subjects in the respective analysis set will be included in the denominator when calculating the percentages irrespective of whether their outcome may be missing.

Handling of complete or partial missing dates for Adverse Events or reported Concomitant Medication will be given in the following Section.

All other missing data will not be imputed.

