### 4.9.4 Key Secondary and Exploratory Efficacy Analyses

Secondary and exploratory endpoints will be analyzed according to the type of endpoint as described below. If data are sparse for any of the exploratory endpoints, summaries may be limited to descriptive statistics of available data or listings only as appropriate.

Time to event endpoints will be analyzed using Kaplan Meier method. The total number of patients with an event, the total number censored and Kaplan-Meier survival estimates with associated 95% CI (25% percentile, median, and 75% percentile) will be presented by treatment group. Further, crude proportions for having the event at timepoints with events observed (derived as: cumulative number of subjects with events / number of subjects in treatment group at baseline) along with 95% Wilson Score intervals with continuity correction will be provided.

Further, Kaplan-Meier estimates at 5, 6, 7, 10, 14 and 28 days from first study drug administration will be provided with associated 95% CI.

A survival plot will be produced with the probability of an event (0% to 100%) along the Y-axis and time in days along the X-axis.

The hazard ratio of ATYR1923 1 mg/kg versus Placebo, ATYR1923 3 mg/kg versus Placebo, and ATYR1923 Total versus Placebo with corresponding 95% CI and p-values will be estimated from a single Cox Proportional Hazards model.

All efficacy summaries and analyses will be based on mITT Set, unless otherwise stated.

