##### Time to recovery

Time to recovery is calculated as:

date of first time WHO scale score  $\leq 3$  - study drug administration date; or date of discharge from hospital - study drug administration date, whichever occurs first.

In the case that a patient does not reach WHO scale score  $\leq 3$  criteria, the patient will be censored at EOS visit.

Additionally, time to recovery will be analyzed using an adapted derivation:

date of first time WHO scale score  $\leq 3$  – randomization date or date of discharge from hospital  $\leq 3$  – randomization date, whichever occurs first. Related output will be noted as sensitivity analysis.

Time to recovery will be analyzed based on mITT and EE Set. Sensitivity analysis for time to recovery will be analyzed based on mITT only.

Time to recovery with WHO scale score  $\leq 3$  without supplemental oxygen

Some patients were discharged from hospital while still using supplemental oxygen and so an additional sensitivity analysis will be performed to evaluate the impact for time to recovery. The following Pseudo-Code will be applied in the given order to derive time to recovery without supplemental oxygen:

1. Derive time to event 'T' as date of first time WHO scale score  $\leq 3$  - study drug administration date; or date of discharge from hospital - study drug administration date, whichever occurs first.
2. For subjects who discharged earlier than reporting an WHO scale score  $\leq 3$  apply the following checks:
  - a. If an supplemental oxygen dose of '0' is reported at day of discharge keep T.
  - b. If an supplemental oxygen dose of '0' is already reported one day prior day of discharge use T-1.
  - c. If an supplemental oxygen dose of  $>0$  is reported at day of discharge and discharge reason indicate that the subject is not on oxygen (e.g. "On Room Air" or "Weaned off O2") keep T.
  - d. If an WHO scale score  $\geq 4$  is reported at day of discharge and an WHO scale score  $\leq 3$  is reported one day after discharge use T+1.
  - e. If an WHO scale score  $\geq 4$  is reported at day of discharge and an WHO scale score  $\leq 3$  is reported two days after discharge use T+2.
  - f. If an WHO scale score  $\geq 4$  is reported at day of discharge and none of the criteria above are met use T+2.
3. In the case that a patient does not reach WHO scale score  $\leq 3$  criteria or has no discharge event, the patient will be censored at EOS visit.

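### No SAP rule gives patients discharged alive on Days 2-4 a Day 5 WHO score, so both Day 5 regressions, as written, leave out the earliest discharges

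*SAP*

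**What the plan says.** SAP 4.9.4.1, under the change from baseline in WHO score, plans two models on the mITT set: "Simple Ordinal logistic regression on the WHO Scale score at each visit (Days 5, 7, 14, 28, and 60) will be performed", and a Firth logistic regression of scores 0-3 versus 4-8 at the same visits.

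Four other provisions decide who has a Day 5 score:

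- **SAP 3.1.1.** In-hospital assessments fall on Days 2-7, 10 and 14. A discharge on a scheduled day replaces that day's visit, and the patient moves to telephone follow-up: "outpatient TC follow-up visits are to be conducted on Day 7 (as applicable) and Day 14".
- **SAP Table 2.** Telephone contacts map only to Days 7, 14, 28 and 60. The earliest window, Day 7 plus or minus 2 days, absorbs a call made on Day 5.
- **SAP Table 3**, "Analysis Visit Window for unscheduled Discharge visits", maps only to Days 7, 10, 14, 28 and 60. Under SAP 4.2, telephone and Discharge visits outside every window are listed only.
- **SAP 4.3.1.** After the adverse-event rules and a denominator rule for percentages: "All other missing data will not be imputed".

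The stacked bar charts have the same limit: "These figures will only consider scheduled assessments and in case the scheduled assessment is not available the mapped unscheduled TC follow up assessments".

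Elsewhere in SAP 4.9.4.1, discharge is itself a favourable event. Recovery is a WHO score of 3 or less or "discharge from hospital, whichever occurs first) by Day 14 and by Day 28 will be presented". Time to recovery and time to improvement also count discharge as an event.

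**The concern.** Day 5 is a named time point of a protocol secondary endpoint. The patients missing from its regressions are missing because they went home early, an outcome after randomisation that treatment may affect. The groups compared are then no longer the randomised groups. If one arm discharges earlier, that arm loses more of its best outcomes.

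One report could therefore show early recovery in its time-to-event outputs and little difference in its Day 5 regressions, only because of who was left out. The SAP does not say how a discharged patient enters these models, so a reader would have to infer the exclusion from four separate provisions.

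**Working it through.** **Step 1: visit mapping (SAP 3.1.1, Tables 2 and 3).**

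| Discharge day | Analysis visits with a WHO score | Day 5 score? |
|---|---|---|
| 2 | 2, 7, 14, 28, 60 | no |
| 3 | 2, 3, 7, 14, 28, 60 | no |
| 4 | 2, 3, 4, 7, 14, 28, 60 | no |
| 5, 6 or 7 | include 5 | yes |

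A discharge on Day 5 itself counts at Day 5, because it falls on a scheduled day and Table 3 covers only unscheduled Discharge visits. A regression cannot use a patient with no response, and the denominator rule in SAP 4.3.1 supplies none. LOCF is in the SAP's abbreviation list, but no rule uses it. The same patients drop out of the bars on days without a contact (among Days 3-6 and 10, depending on discharge day).

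**Step 2: expected effect.** The documents state no Day 5 figure, effect size or discharge rate, so there is nothing to reproduce and every rate below is assumed. Let d be the placebo share discharged by Day 4, F any placebo cumulative share at or below a cut-point, and OR the true odds ratio. Assume proportional odds with all early discharges in the best category.

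- Drug arm: F becomes OR·F/(1+(OR−1)F), and d becomes OR·d/(1+(OR−1)d).
- After dropping the discharged, the odds at each cut-point are (F−d)/(1−F) on placebo and OR(F−d)/[(1−F)(1+(OR−1)d)] on drug.
- The ratio is OR/(1+d(OR−1)) at every cut-point, so it holds for both the ordinal and the 0-3 versus 4-8 model.

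| d (placebo) | Early discharges on drug at OR 3 | Analysed OR, true 3 | Analysed OR, true 2 |
|---|---|---|---|
| 0% | 0% | 3.00 | 2.00 |
| 5% | 0.15/1.10 = 13.6% | 3/1.10 = 2.73 | 2/1.05 = 1.90 |
| 10% | 0.30/1.20 = 25% | 3/1.20 = 2.50 | 2/1.10 = 1.82 |
| 20% | 0.60/1.40 = 43% | 3/1.40 = 2.14 | 2/1.20 = 1.67 |

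A true OR of 1 stays 1.

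**Step 3: a single trial of 10 per arm.** With treatment as the only term, the Firth estimate adds 0.5 to each cell. Two invented examples, with approximate 95% intervals:

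- *Falls.* 5/10 v 3/10 at 0-3 gives (5.5/5.5)/(3.5/7.5) = 2.14 (0.38 to 12.1). Dropping 4 drug and 2 placebo discharges leaves 1/6 v 1/8: (1.5/5.5)/(1.5/7.5) = 1.36 (0.11 to 16.9).
- *Rises.* 6/10 v 3/10 gives (6.5/4.5)/(3.5/7.5) = 3.10 (0.54 to 17.8). Dropping 2 per arm leaves 4/8 v 1/8: (4.5/4.5)/(1.5/7.5) = 5.00 (0.56 to 44.5).

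All outcomes were enumerated at a true OR of 3, with a further 10% of placebo in hospital at score 3. Dropping early discharges raises the Firth OR in 31.7% of trials at d = 10% and 30.5% at d = 20%. It lowers the OR in 61.7% and 64.8%, and leaves it unchanged in the rest.

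**Step 4: error rates at the 5% level, all patients kept versus dropped.** Firth results are exact (penalised likelihood-ratio test). Ordinal results come from 2,000 simulated three-arm trials per scenario, with 1 mg/kg given half the log odds ratio and a likelihood-ratio test of 3 mg/kg versus placebo. The Monte Carlo standard error is at most 1.1 points.

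| | d = 10% | d = 20% |
|---|---|---|
| Firth power, OR 3 | 16% to 6% | 20% to 5% |
| Ordinal power, OR 3 | 31% to 19% | 28% to 14% |
| Firth null rejection | 3% to 1% | 4% to 1% |

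Ordinal null rejection is 6% either way.

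**Step 5: candidate rules at d = 20%, true OR 3 (dropping gives 2.14).** Scoring every early discharge in one category within 0-3 returns 3.00 by construction. If 10, 25 or 50% are instead still scored 4 at the first call, the ordinal OR is 2.87, 2.71 or 2.50. In the collapsed model, 25% scored 4 gives 25% v 45.5% at 0-3, OR 2.51. With 50% it gives 20% v 34.8%, OR 2.14, no better than dropping.

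**The case against.** *A score may exist even though no rule supplies one.* By-visit summaries use the visit as reported in the eCRF. Protocol 8.3.2 asks for the date and time of changes in ambulatory status and oxygen need, and the oxygen-free recovery derivation in SAP 4.9.4.1 uses WHO scores one and two days after discharge. This stands as a limit on wording. The supported statement is that no SAP rule provides a Day 5 score, not that none was ever recorded.

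*The trial is small and exploratory.* SAP 3.1.4 makes no power calculation, and SAP 4.9.2 treats all p-values as exploratory. The affected models cover one visit of five. All of this stands and limits the weight of the point.

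*Other outputs keep these patients.* SAP 4.9.4 states: "Kaplan-Meier estimates at 5, 6, 7, 10, 14 and 28 days from first study drug administration will be provided", with crude proportions on full arms. Time to improvement by at least 1 and at least 2 points counts discharge as an event, and the Day 7 models include these patients by telephone. These are useful whole-cohort checks, and the recovery outputs come close to the 0-3 versus 4-8 contrast at Day 5. None is the full-scale ordinal comparison at Day 5.

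*The by-visit table prints n.* That makes the gap visible there, but does not correct the odds ratio.

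*Assigned scores have their own weakness.* This stands: "Some patients were discharged from hospital while still using supplemental oxygen", so counting every discharge as 0-3 may be generous. It calls for a sensitivity analysis.

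A reader might infer that the Day 5 odds ratio must be biased toward no effect in this trial. The documents do not support that. They give no discharge rates by arm, attenuation is an expectation under the assumptions of step 2, and at about 10 per arm nearly a third of simulated trials move the other way.

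**Conclusion.** The point holds as a gap in the plan. Read together, SAP 3.1.1, 4.2, 4.3.1 and Tables 2 and 3 exclude patients discharged alive on Days 2-4 from both Day 5 regressions, because of a favourable outcome that the same SAP treats as recovery.

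The expected attenuation of a true odds ratio of 3 ranges from none (no early discharges) to 2.14 (20% of placebo discharged by Day 4). It rests on assumed rates, proportional odds and all early discharges being in the best category. The higher rate implies 43% of the drug arm home by Day 4, which may be high for patients enrolled with severe pneumonia. The cost is loss of power and an informatively selected comparison, without an inflated false-positive rate.

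Two wider readings should be set aside. The later visits are not affected by this route, because early discharges are scored by telephone at Days 7, 14, 28 and 60 (Protocol Table 1, footnote 1). Nor does the gap undermine the trial's conclusions: the primary objective is safety, and the time-to-event outputs retain these patients. It is worth correcting because the correction is cheap and the plan is otherwise silent.

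**What to change.** State one rule and use it everywhere at Day 5. Keep mITT patients discharged alive on Days 2-4 and not readmitted by Day 5 in both models. Assign them a single discharged category within 0-3 (for example score 2, ambulatory), in line with the SAP's recovery definition. Use that same value in the Firth model, the ordinal model, the Day 5 table and the bar charts. A patient back in hospital on Day 5 keeps the observed score.

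As a sensitivity analysis in both models, use the first post-discharge telephone score, or the Discharge-assessment score if there was no call, so that patients sent home on oxygen can count as 4. Show the planned observed-case models beside these, labelled as such, with n per arm.

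The cost is SAP wording and programming, with no new data collection. There are three downsides. The Day 5 value is assigned, not observed. The telephone score usually comes from Days 5-9 and so may postdate Day 5. And because SAP versions 2.0 and 3.0 already contain changes made after unblinding, the new outputs must be labelled post-unblinding or post hoc, consistent with SAP 3.2.
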